Study Title: Geniculate Artery Embolization for the Treatment of Knee Osteoarthritis 04/08/2025

G190248 Supplement 001

A. Cover Page

Device Information : Device name: Teleflex Gel-Bead

Intended use of device:

The Gel-Bead embolization particles will be used to perform geniculate artery embolization (GAE) for the purposes of treatment of osteoarthritis-related knee pain.

Device Information:

Device name: Teleflex Gel-Bead

Intended use of device:

The Gel-Bead embolization particles will be used to perform geniculate artery embolization (GAE) for the purposes of treatment of osteoarthritis-related knee pain.

Sponsor-Investigator and Correspondent Contact Information:

[name] University of Pittsburgh Medical Center [name] [contact] / [contact] [contact]

Manufacturer Information:

Teleflex (acquired Vascular Solutions, Inc. February 2017) [name] [contact]

Distributed by Medtronic

Referenced files: There are no referenced files.

Protocol Ammendments:

Updated protocol to remove 6-minute walk test due to feasibility issues in performing

B. Clinical Plan

The primary goal of our investigation is to determine if geniculate artery embolization (GAE) will result in a decrease in pain and disability caused by knee osteoarthritis. The investigation will be conducted as two distinct studies:

 A pilot study of GAE for the treatment of knee osteoarthritis
 A series of up to 30 subjects undergoing geniculate artery embolization will be included in this arm with the explicit purpose to demonstrate safety and efficacy.

The primary endpoint of this study is overall efficacy of treatment as determined by a minimal clinically significant improvement in KOOS pain score of 10 based on the KOOS Pain questionnaire at 6 months.

Secondary outcomes will be improvement in functionality and quality of life based on the KOOS Function in Sport and Recreation, and KOOS Quality of Life Scales. Secondary outcomes will also include changes in quantitative functional metrics as well as reduction in medication use.

Technical success will be defined as the performance of diagnostic angiography of the knee with delivery of the Gel-Bead particles to a region of hypervascularity within the knee resulting in reduced flow/occlusion of the target vessels. Clinical success will be defined by a decrease in pain of 10 points per the KOOS questionnaire at 6 months.

C. Report of Prior Investigations of the Device

Name of the Investigational Device: Gel-Bead Microspheres

Intended Use of the Device: Geniculate artery embolization (GAE) for patients with osteoarthritis of the knee.

Description of the Investigational Device

Gel-Bead embolization spheres were found to be substantially equivalent and cleared medical devices (Premarket Notification K133237) to prior technologies:

- Embosphere Microspheres (Biosphere Medical, Inc/Merit Medical Systems, Inc, K021397)
- Gel-Block Embolization Pledgets (Vascular Solutions, Inc, K113266)

Identified in the Code of Federal Regulations 21 Part 870- Subpart D Cardiovascular Prosthetic Devices. Classification Name: Artificial Embolization Device. Class II Medical Device Common Name: Vascular Embolization Device Subpart D-Prosthetic Devices; Sec. 870.3300 Indication for Use: Gel-Bead embolization spheres is intended for use in embolization of hypervascular tumors.

Gel-Bead embolization spheres (Gel-Bead) consist of biodegradable gelatin spheres pre-filled in 20ml syringes. Each syringe contains 1 ml of spheres suspended in 5 ml of saline. There are four size ranges for Gel-Bead offered: 100-300 um, 300-500 um, 500-700 um and 700-1000 um. The spheres are intended to be delivered via a delivery catheter with an inner diameter that is appropriately sized for sphere delivery (not included). The product is intended for single use and is sterilized by Gamma irradiation. The liquid suspension is mixed with iodinated contrast before use to allow visualization under fluoroscopy. Once a catheter has been fluoroscopically guided into the target vessel, the microspheres are injected and cause obstruction at the arteriole level until the desired degree of

embolization is reached. The microspheres used during this study will be unmodified.

A Gel-Bead implantation GLP animal study in twelve mature miniature swine, with animals survived up to 12 weeks following implantation was performed (13). Eight animals received Gel-Bead and four animals were implanted with the control (Embosphere). Gel-Bead spheres were implanted in the selected target arteries with angiography confirmation. There were similar well-demarcated foci of infarction, indicative of successful embolization, observed in the target organs of both test article and control article animals. No clinically significant abnormalities were identified in the clinical pathology blood results. No systemic abnormalities were identified. Verification, animal study, and biocompatibility test results met the specified acceptance criteria and did not raise new safety or performance issues. Gel-Bead was therefore deemed substantially equivalent to the predicate device (Embosphere).

The technological differences between the Gel-Bead and predicate device have been evaluated through bench tests to provide evidence supporting the substantial equivalence of the 100-300 μ m and 300-500 μ m size embolization spheres. The 100-300 μ m and 300-500 μ m sizes are substantially equivalent to the specified predicate device based on comparisons of the device functionality, technological characteristics, and indications for use. The device design has been verified through the following tests: deliverability, sphere diameter, sphericity. Gel-Bead received 510(k) clearance from the FDA in April 2014 for the user of embolization of hypervascular tumors. Early trials have shown transcatheter embolization of abnormal neovasculature with particles can be effective in the treatment of mild to moderate knee osteoarthritis refractory to conservative management in select cases (5).

Transcatheter arterial embolization with microparticles has been shown to be safe in early trials for treatment of knee osteoarthritis as well as in patients being treated for hemarthrosis, with small trials showing no major complications related to particle embolization (5, 8-9). Additionally, complications do not increase with repeat embolizations (9). A theoretical advantage of Gel-Bead is the biodegradable nature, in contrast to other permanent microsphere devices, which remain permanently inside the patient.

Bibliography

1.0 Purpose of the Investigation

Osteoarthritis is an increasingly prevalent disease and often results in functionally limiting joint pain. In 2015, an estimated 54 million adults (22.7%) in the United States had doctor-diagnosed arthritis, with 43.5% of those patients reporting lifestyle and activity limitations (1).

The knee is a commonly affected joint and results in an annual healthcare expenditure of \$27 billion (2). Definitive therapy for knee osteoarthritis is total knee arthroplasty. An estimated 54% of patients with knee osteoarthritis require a total knee arthroplasty within their lifetime, and 658,000 people undergo surgery annually (2-3). The goal of conservative management is to delay or eliminate the need for a total knee arthroplasty in patients. Currently, patients manage their pain with conservative management for an average of 13 years (2).

First line conservative management is treatment with physical therapy, weight loss, non-steroidal antiinflammatory medications, and corticosteroid injections. Opiate medications are being prescribed with increasing frequency, despite evidence that they do not effectively treat osteoarthritis pain (4).

Early trials have shown transcatheter embolization of abnormal neovasculature with microparticles can be effective in the treatment of mild to moderate knee osteoarthritis refractory to conservative management in select cases (5). This therapy aims to treat the angiogenesis and inflammatory component involved in the pathophysiology of osteoarthritis (6-7).

Thickening and hypertrophy of the knee synovium has a similar appearance on angiography to hypervascular tumors. Transcatheter arterial embolization with permanent and resorbable particles has been shown to be safe in early trials for treatment of knee osteoarthritis as well as in patients being treated for hemarthrosis, with small trials showing no major complications and 8-20% having minor self-resolving skin or puncture site complications (5, 8-9). Additionally, complications do not increase with repeat embolizations (9). The use of resorbable particles has a theoretical advantage as the particles will not permanently reside within tissue.

1.1 Trial Objective

The purpose of this study is to perform a pilot to determine efficacy of transcatheter arterial embolization of the geniculate arteries in treating knee osteoarthritis related pain using the Gel-Bead embolization particles. This trial will assess reduction in pain, functional improvement, and reduction of medication usage in patients with mild to moderate knee osteoarthritis who have failed conservative management.

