2.2.1 General Study Design

A series of 15 patients undergoing geniculate artery embolization will be included in this arm with the explicit purpose to demonstrate safety and efficacy.

This trial will assess reduction in pain, functional improvement, and reduction of conservative medical therapy in patients with mild to moderate knee osteoarthritis who have failed conservative

management, for 6 months and for up to two years following embolization.

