2.3.1 General characteristics of the proposed subject population

Similar to prior studies conducted on GAE, subjects included in the study will be those with mild to moderate knee osteoarthritis with moderate to severe pain that is refractory to conservative management. These are patients who have significant symptoms but are not ideal candidates for total knee replacement.

2.3.2 *Anticipated number of research subjects*

For the Pilot Study, 30 patients are expected to enroll (defined as completion of the informed consent process as per University IRB policies) and all are expected to complete the study.

2.3.3 Inclusion Criteria:

1. Patients between ages 18 and 75 with moderate/severe knee pain secondary to primary osteoarthritis. Moderate/severe pain will be defined as pain 30 mm to

100 mm on the Visual Analog Pain Scale (where 0 denotes 'no pain' and 100 mm denotes worst pain imaginable')

- 2. Grade 1, 2, or 3 osteoarthritis on the Kellgren-Lawrence grading scale on knee x-ray in the last 12 months
- 3. Pain must be refractory to 3 months of medical management (which may include a combination of oral analgesics, intraarticular steroids, viscosupplementation, opioid therapy, etc)
- 4. Patients willing and able to consent to the study

2.3.4 Exclusion Criteria:

- 1 Kidney dysfunction defined as an estimated GFR < 60 mL/min
- 2 Acute knee injury
- 3 Current local infection
- 4 Prior ipsilateral knee replacement surgery
- 5 Infectious or inflammatory arthritis
- 6 History of contrast allergy resulting in anaphylaxis
- 7 INR (International Normalization Ratio) > 1.6
- 8 Platelets < 50,000
- 9 Significant atherosclerosis that would limit angiography
- 10 Active malignancy
- 11 Active pregnancy
- 12 Appropriate candidate for knee replacement surgery determined by clinical and physical examination
- 13 Recent within 3 months, or active cigarette user
- 14 Any other condition that in the opinion of the investigator would preclude the patient from participation.

2.4 Study Procedures:

2.4.1 Patient Recruitment:

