2.5.2 Sample Size Determination

The Knee Injury and Osteoarthritis Outcome (KOOS) Score which is a primary outcome measure is a measure of patients' knee and associated problems and functionality. It is endorsed by the American Academy of Orthopedic Surgeons, the US Food and Drug Administration, and the International Cartilage Repair Society and has demonstrated reliability for both clinical and research purposes (11). The Visual Analog Scale (VAS) for pain will be used as a secondary outcome measure. This scale is also well-validated and has demonstrated reliability for patients with osteoarthritis (12). The Minimal Clinically Important Difference (MCID) for KOOS has been reported to be ~10. Data on the KOOS indicates a population standard deviation of 15 (koos.nu). Assuming we wish to detect an MCID of 10 points in this population, our targeted effect size is 0.66. A power calculation for a paired t-test (baseline vs 6-month KOOS Pain scores) shows our pilot study of 15 patients would have 22% power.

2.5.3 *Efficacy Analysis*

Comparison of semi-quantitative and quantitative outcome measures will be performed with the appropriate statistics testing. For the pilot group, baseline and endpoint scores will be compared using paired t-tests.

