3.0 Risk Analysis

3.1 Anticipated Risks

To mitigate risk to patient confidentiality, data will be kept in encrypted files on a secure UPMC server. The identifying patient information will be kept in a second document separate from the clinical data gathered, and a non-identifying code will be assigned to each patient. The data collected will not be shared with any person(s) not included in the study investigator list. Should a breach of conduct occur, the IRB will be notified immediately by one of the principal investigators.

Participants in the intervention arm will undergo an invasive procedure and will be subjected to moderateto-high risk. Risks include but are not limited to bleeding at the puncture site, infection, damage to nearby structures, synovitis, worsening of groin hematoma, and nontarget embolization. A qualified, boardcertified interventional radiologist will perform the procedure. Sterile technique will always be followed. Radiation exposure to the patient will be minimized using standard strategies (e.g. aggressive collimation, minimizing fluoroscopy time). All adverse events will be thoroughly documented and reported to the UPMC IRB immediately.

Because the study population has osteoarthritis-related knee symptoms refractory to conservative management, the next treatment option traditionally available is knee replacement surgery. Transarterial embolization, while still an invasive procedure, has a much lower risk profile that knee replacement surgery.

This trial will include 15 initial patients to confirm safety and initial efficacy of the treatment. Patients will include both male and female and range from age 18-75 who meet the inclusion criteria as detailed above. GAE will be performed by the trained investigating Interventional Radiologists who have significant experience in performing endovascular embolization procedures.

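### The aims say the pilot will determine efficacy and demonstrate safety, but a single treated series of 15 to 30 patients can only estimate change from baseline and bound event rates loosely

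*Combined protocol and SAP*

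**What the plan says.** The aim appears in four places.

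- Section 1.1 (Trial Objective): "The purpose of this study is to perform a pilot to determine efficacy of transcatheter arterial embolization of the geniculate arteries".
- Section B (Clinical Plan), for "A series of up to 30 subjects undergoing geniculate artery embolization": "with the explicit purpose to demonstrate safety and efficacy".
- Section 2.2.1, which gives the design: "A series of 15 patients undergoing geniculate artery embolization will be included in this arm with the explicit purpose to demonstrate safety and efficacy".
- Section 3.1 (Anticipated Risks), in softer terms: "15 initial patients to confirm safety and initial efficacy of the treatment".

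The size of the series is 15 in sections 2.2.1, 2.5.2 and 3.1. It is up to 30 in section B, and section 2.3.2 says "For the Pilot Study, 30 patients are expected to enroll" and that "all are expected to complete the study".

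Under the GAE visit in section 2.4, every subject is treated with Gel-Bead. No control arm, randomization or blinding is described anywhere in the text. Section 2.5.1.1 makes an improvement of at least 10 points in KOOS Pain at 6 months the primary endpoint, calls it overall efficacy, and states a hypothesis comparing GAE with sham. The only efficacy test specified for the pilot is in section 2.5.3: "For the pilot group, baseline and endpoint scores will be compared using paired t-tests". Section 2.5.4 reports adverse events in the pilot descriptively and sets no target rate or acceptance limit.

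**The concern.** To determine or demonstrate efficacy is to say that the treatment caused the improvement. A comparison of each patient with his or her own baseline does not isolate that cause. Patients are selected for pain at entry (VAS 30 mm or more, section 2.3.3), so some regression to the mean is possible. They have an invasive procedure and then rate their own pain, with no masking described. Symptoms may also fluctuate naturally over 6 months. The paired test puts all of this and any GAE effect into one number, and it tests that number against zero change, not against 10 points.

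Replacing the sham hypothesis with a within-patient one would make the hypothesis match the test. The aims would still promise more than the test can deliver.

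On safety, demonstrating or confirming has no defined meaning without a criterion, and a series of this size leaves wide limits on any event rate. At stake is what the trial can legitimately conclude.

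**Working it through.** **Inputs from the documents.** N = 15 or 30 (above). Threshold 10 points and SD 15 (section 2.5.2). Standardized effect 0.66 (section 2.5.2). Two-sided test (section 2.5.1.1). Stated power 22% for a paired t-test with 15 patients (section 2.5.2).

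**Assumptions.** Alpha 0.05 for the primary test, because the plan gives 0.05 only for the adverse-event chi-square test. SD of change: the plan's 15 is a population SD, and no SD of change is given. If 15 is the SD at each visit and ρ is the correlation between visits, the SD of change is 15 × √(2(1−ρ)). That is 15 at ρ = 0.5 and 21.2 at ρ = 0. I use 15 as the central value and 12 to 21.2 as the range. The non-specific gains in step 3 are assumptions as well.

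**Step 1. The plan's own figure.** Power of a paired t-test from the noncentral t distribution, n = 15, d = 0.66: noncentrality 0.66 × √15 = 2.56, critical value 2.145, power 66% (67% with d = 10/15). At n = 30 it is 94%. The stated 22% does not reproduce. A two-sample t-test splitting 15 patients 7 and 8 gives about 22%, so the figure fits a parallel-group comparison. On the plan's own inputs, a significant paired result is therefore more likely than section 2.5.2 suggests.

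**Step 2. Smallest observed mean change that is significant.** This is t(0.975, n−1) × SD/√n, which is also the half-width of the 95% CI.

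| SD of change | n = 15 | n = 30 |
|---|---|---|
| 15 | 2.145 × 15/√15 = 8.3 | 2.045 × 15/√30 = 5.6 |
| 21.2 | 2.145 × 21.2/√15 = 11.7 | 2.045 × 21.2/√30 = 7.9 |

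At SD 15, both values are below 10. At SD 21.2 that is true only for n = 30.

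**Step 3. Illustration: no GAE effect, but every patient's expected score rises by m points for other reasons.** The probability of p<0.05 comes from the noncentral t with noncentrality (m/SD) × √n. For m = 5 and SD 15 this is (5/15) × √15 = 1.29 at n = 15 and (5/15) × √30 = 1.83 at n = 30.

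| m | SD of change | n = 15 | n = 30 |
|---|---|---|---|
| 5 | 12 | 32% | 60% |
| 5 | 15 | 23% | 42% |
| 5 | 21.2 | 14% | 24% |
| 8 | 15 | 49% | 81% |
| 8 | 21.2 | 28% | 51% |

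The larger series gives the higher probability, because extra patients sharpen the test of change without adding a comparator.

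**Step 4. Precision of the responder proportion.** Exact (Clopper-Pearson) 95% limits, taking 60% responders as an example: 9/15 gives 32-84%, and 18/30 gives 41-77%.

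**Step 5. Safety.** With zero events of a given type, the one-sided 95% upper limit is 1 − 0.05^(1/n).

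- n = 15: 1 − 0.05^(1/15) = 18.1%.
- n = 30: 1 − 0.05^(1/30) = 9.5%.

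A complication with a true rate of 5% would not be seen at all with probability 0.95^15 = 46% or 0.95^30 = 21%.

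**The case against.** The protocol calls this a pilot, section 3.1 speaks only of initial efficacy, and sections 1.1 and 2.2.1 also say the trial will assess reduction in pain, which is descriptive. Any uncontrolled pilot has this limitation. That softens the point but does not answer it: no section says that causal inference is limited, and the word pilot supplies no comparator. Nor does the sham hypothesis in section 2.5.1.1, for which no arm is described.

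A reader might infer that a significant paired test would be reported as proof of efficacy, or used to justify wider use in place of a controlled trial. The documents do not support that. They contain no such decision rule and set no alpha for this test. Clinical success is defined in section B as a 10-point change, not as bare significance. Section B also announces two distinct studies, and a sham mean is named, so a comparative study appears to have been considered.

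A reader might also infer that the safety analysis over-claims. It does not: section 2.5.4 already plans descriptive reporting for the pilot. The excess is in the aims, and only the exact intervals are missing from the analysis.

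The objection that the step 3 percentages rest on assumed gains and an assumed SD of change stands in full. They are an illustration, not an estimate of an error rate for this trial. The absence of blinding is also an inference from the text, because the design schematic could not be seen.

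**Conclusion.** The point holds as a mismatch between the stated aims and the described design. It is worth correcting, but it is not a fault in running an uncontrolled pilot, and it is no evidence about whether GAE works.

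That a paired test cannot attribute change to GAE needs no numerical assumption. That significance can be reached below the 10-point threshold depends on the SD of change: with SD 15 it holds at both sample sizes (8.3 and 5.6 points), and with SD 21.2 only at 30 patients (7.9 against 11.7 at 15). The false-attribution range of 14-32% at 15 patients and 24-60% at 30 depends on a 5-point non-specific gain that the documents do not give. The safety limits of 18% and 9.5% follow from the sample sizes alone, and they are too wide to call safety demonstrated or confirmed.

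**What to change.** 1. In sections B, 1.1, 2.2.1 and 3.1, replace the efficacy aim with estimation: the mean 6-month change in KOOS Pain and the proportion of patients improving by at least 10 points, each with a 95% CI, to inform a controlled trial.
2. In the same sections, replace the safety aim with describing adverse event rates. Add to section 2.5.4 that each rate is given with an exact 95% CI, including for types with zero events.
3. Add to section 2.5.3 that a significant within-patient change will be described as change from baseline, not as efficacy of GAE.
4. State the expected precision for one sample size once 15 and 30 have been reconciled, and either remove the sham hypothesis or describe the comparator it refers to.

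The cost is protocol wording and a few intervals in the report. No patients, visits or procedures are added. The downside is a more modest claim.

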2.0 GAE Study Clinical Protocol

2.0 Title and Version Date of Clinical Protocol: Geniculate artery embolization for the treatment of osteoarthritis of the knee Version date: 4/18/2023

2.2 Study Design:

[figure not shown]
2.2.1 General Study Design

A series of 15 patients undergoing geniculate artery embolization will be included in this arm with the explicit purpose to demonstrate safety and efficacy.

This trial will assess reduction in pain, functional improvement, and reduction of conservative medical therapy in patients with mild to moderate knee osteoarthritis who have failed conservative

management, for 6 months and for up to two years following embolization.

